### **3.2 Number of Subjects**

12 subjects will be enrolled in this study.

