# 7 Statistical Plan

## 7.1 Sample Size Determination

Data analysis: Due to the costs associated with a study, we propose a single armed study of 12 subjects with corollary science including RNA sequencing. This will reduce costs and provide

biomarkers predictive of response. Effect sizes will be estimated for the appropriate statistical tests that will be used for group comparisons in future studies. This will enable more accurate power and sample size estimates moving forward.

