## 7.2 Statistical Methods

### Descriptive Statistics

#### Sample Size Computation and Power Analysis:

The sample size for this pilot study is set at 12 subjects for logistical and financial reasons. This is similar in size to other exploratory studies and will provide adequate data for estimation purposes for planning future studies. With 12 subjects, the study is intended to be for estimation purposes only.

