### Bioinformatic Analysis:

RNA-seq analysis: We will use our recently developed LinNorm program

to process RNA-seq data and detect differentially expressed genes (DEGs) by comparing the RNA-seq profiles. We will first find DEG between responsive and non-responsive samples from the same individual by using paired or unpaired Wilcoxon rank-sum test (depending on how the samples are collected). We will then rank each gene in the DEGs based on the occurrence frequencies in all 12 subjects to find common DEGs for responsiveness (use permutation test to determine the p value). By comparing the normal tissue with the pathogenic tissue (responsive + non-responsive) using the above approach, we will detect a common DEGs for NL pathogenesis. Hierarchical clustering and Principal Component Analysis (PCA) will be applied to samples for their hierarchical relationship and clustering properties. Ideally normal, responsive and non-responsive tissues should form three distinct groups. The PCA analysis will provide us a set of gene signatures that can distinguish these three types of tissues. The common DEGs for responsiveness and pathogenesis, as well as gene signature from PCA will be used for our pathogenesis or survival

prediction. Additionally, we will perform de-convolutional analysis, to compare the immune profiles of responsive and non-responsive tissue and to correlate immune profiles. Predictive biomarkers will be correlated with lesional and global responses.

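### Genes are selected on response in all 12 subjects and then correlated with response, with no independent sample named, so the reported correlations cannot show prediction

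*Combined protocol and SAP*

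**What the plan says.** Section 3.2 states that "12 subjects will be enrolled in this study". Section 7.2 adds that "The sample size for this pilot study is set at 12 subjects for logistical and financial reasons" and "With 12 subjects, the study is intended to be for estimation purposes only". Section 7.1 nevertheless gives "biomarkers predictive of response" as one of the things this design will provide.

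The Bioinformatic Analysis part of Section 7.2 starts with selection: "We will first find DEG between responsive and non-responsive samples from the same individual by using paired or unpaired Wilcoxon rank-sum test", the choice of test depending on how tissue is obtained. It will then "rank each gene in the DEGs based on the occurrence frequencies in all 12 subjects" to find common responsiveness genes, with a permutation p value for that ranking. A PCA is to give a signature that tells normal, responsive and non-responsive tissue apart. The common genes, "as well as gene signature from PCA will be used for our pathogenesis or survival" prediction. The last step is: "Predictive biomarkers will be correlated with lesional and global responses". The Exploratory Objectives in Section 2 name the global response measures as NL Lesion Score, PGA and BSA.

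Section 3.1 gives three biopsies per subject: one lesional and one non-lesional at week 0, and one from a treated lesion at week 4.

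**The concern.** Response is used twice. It decides which genes are kept, and response in the same people then judges those genes. A correlation obtained this way contains the effect of having searched a whole transcriptome for genes that fit 12 outcomes. It would be large even if no gene carried information.

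At stake is the choice of markers for the next trial. The study is for estimation, and an estimate inflated by selection fails that purpose. A reader of the final report could not tell a real marker from a chance one.

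Two further statements weaken the prediction aim. Survival is named as a prediction target, but Sections 3.4 and 3.5 list only NL score, pruritus NRS, Skindex-16, PGA, BSA and lesional volume. The tissue for the response contrast is placed at week 12 in the Study Summary and in the Exploratory Outcome Measures of Section 3.1. It is placed at week 4 in the Section 2 Exploratory Objectives, the biopsy text of Section 3.1 and Table-2.

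**Working it through.** **Inputs from the plan.** There are 12 subjects, with no formula, alpha, power or effect size behind that number, so there is no sample-size figure to reproduce. The stated maximum of 36 tissue samples does reproduce: 12 subjects × 3 biopsies = 36.

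**Assumptions.** The plan gives no gene count for this trial. Section 3.1 specifies transcriptome sequencing, so 10,000 to 20,000 genes are assumed. The 594-gene panel from the earlier work in Section 1.1 serves only as a low bound. The plan does not define responsive, so a 6/6 split is assumed, with other splits shown. A signature of 10 genes is also assumed.

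**Step 1: where the contrast falls.** Each subject supplies one treated-lesion biopsy. No subject can supply both a responsive and a non-responsive treated sample, so the contrast is between at most 12 subjects.

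**Step 2: perfect separation by chance.** For a gene unrelated to response, the probability of separating k responders from 12 − k non-responders perfectly is 2/C(12, k). Multiplying by the number of genes gives the expected count.

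| Split | Probability per gene | 594 genes | 10,000 genes | 20,000 genes |
|---|---|---|---|---|
| 6/6 | 2/924 = 0.00216 | 1.3 | 22 | 43 |
| 4/8 | 2/495 = 0.00404 | 2.4 | 40 | 81 |
| 3/9 | 2/220 = 0.00909 | 5.4 | 91 | 182 |

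In null simulations with a 6/6 split, at least one perfect separator appeared in 98–100% of trials at 10,000 to 20,000 genes and in 51–74% at 594. The lower figures come from strongly correlated genes.

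**Step 3: best single gene under the null.** These are simulated best |Pearson r| values with a discretised NL-score change.

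| Genes | Median (5th–95th percentile), independent genes | Median, strongly correlated genes |
|---|---|---|
| 594 | 0.82 (0.76–0.91) | 0.78 |
| 10,000 | 0.90 (0.87–0.94) | 0.87 |
| 20,000 | 0.91 (0.88–0.95) | 0.90 |

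An unadjusted two-sided p < 0.05 at n = 12 needs only |r| > 0.576.

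**Step 4: a selected signature under the null.** Ten genes were selected on response and combined. In the same 12 subjects the signature classified 100% correctly and had mean r of 0.76 to 0.79 with the continuous response. In new subjects it classified 50% correctly, with mean r of 0.00.

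**Step 5: selection repeated inside leave-one-out folds.** Mean accuracy fell to 41–43%. This is slightly below the 50% expected by chance because leave-one-out is biased low in balanced null data. Single trials ranged from about 8% to about 80% (5th–95th percentile). The cross-validated correlation is as imprecise: with 5,000 null genes its mean was −0.21 and its 5th–95th percentile range −0.72 to 0.43.

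**Step 6: would a per-gene false discovery rule be enough?** With a 6/6 split the smallest attainable Wilcoxon p is 0.00216. Benjamini–Hochberg at 5% needs k genes at that value with k ≥ 0.0021645 × 20,000 / 0.05 = 865.8, so 866 perfect separators (26 of 594). The rank test on 12 subjects is too coarse for such a rule to be useful.

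**The case against.** **The plan already has a permutation test.** It does, and a reader who infers that there is no safeguard would be wrong. But the text attaches the test to the ranking of common genes. It does not reach the signature or the later correlation, and no rule for multiple genes is stated.

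**Selection is worded as a within-person contrast.** Genes chosen on differences between lesions of one person would not automatically correlate with global response, which varies between persons. This would stand if each subject gave treated samples of both kinds. Section 3.1 does not provide them, and Section 7.2 itself allows an unpaired test. The between-subject reading is still an inference from the biopsy schedule; the plan does not state it.

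**The work is exploratory.** Sections 2 and 3.1 say so, and Section 7.2 limits the trial to estimation. This lowers the weight of the point, since no primary, secondary or safety analysis is affected. It does not remove the bias.

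**PCA does not use response.** That is correct for the components themselves. The bias enters when components or genes are kept because they distinguish the response groups.

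**Cross-validation at n = 12 is very imprecise.** This also stands (step 5). A cross-validated value should therefore not be the only result reported.

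**Conclusion.** The point holds. As written, the correlation between the selected biomarkers and response measures the selection step together with any real signal, and the two cannot be separated. Under a pure null with an assumed 10,000 to 20,000 genes, the best gene reaches about |r| = 0.9 and a 10-gene signature about 0.78 in the same subjects, against 0 in new ones. The Section 7.1 claim is not supported by this analysis.

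A reader might infer that near-perfect markers are bound to appear. The documents do not support that in general. They give no gene count or response split. At 594 genes the best null correlation is about 0.8, and a perfect separator is likely but not certain. A signature correlating at 0.78 is not near-perfect, and the planned permutation test may screen out some genes before the correlation step. The conclusion rests on the between-subject contrast. If all 12 subjects fell into one response class, no selection would be possible.

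This is a change the plan should make. It does not threaten the trial's main results.

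**What to change.** In Section 7.2, Bioinformatic Analysis:

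- Define responsive and non-responsive, and state that the contrast is between subjects.
- Extend the planned permutation test to the whole procedure. Permute response across subjects, and repeat gene selection, signature building and the correlations with NL score, PGA and BSA each time. Judge single genes against the permutation distribution of the maximum correlation across genes. With 20,000 independent null genes the 95th percentile of that maximum is about 0.95, so few or no genes may pass.
- For prediction, use week 0 tissue. Expression in on-treatment tissue is not a baseline predictor.
- Give same-sample correlations only as descriptive and labelled as inflated by selection. Beside each, give a cross-validated value with selection repeated inside every fold, and state its wide uncertainty.
- Replace survival as the prediction target with the trial's response measures.

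In Section 7.1, say that the study will provide candidate biomarkers for validation in independent subjects.

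Reconcile the week 12 tissue statements (Study Summary; Exploratory Outcome Measures in Section 3.1) with the week 4 statements (Section 2; biopsy text in Section 3.1; Table-2).

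The cost is wording and some extra computing, with no new subjects, samples or visits. Reported biomarker performance will look less favourable.

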### 7.3 Subject Population(s) for Analysis

- All-completed population: All subjects that receive at least one dose will be considered for analysis.

## 8 Safety and Adverse Events

### 8.1 Definitions

#### Unanticipated Problems Involving Risk to Subjects or Others (UPIRTSO)

Any unanticipated problem or adverse event that meets the following three criteria:

- Serious: Serious problems or events that results in significant harm, (which may be physical, psychological, financial, social, economic, or legal) or increased risk for the subject or others (including individuals who are not research subjects). These include: (1) death; (2) life threatening adverse experience; (3) hospitalization - inpatient, new, or prolonged; (4) disability/incapacity - persistent or significant; (5) birth defect/anomaly; (6) breach of confidentiality and (7) other problems, events, or new information (i.e. publications, DSMB reports, interim findings, product labeling change) that in the opinion of the local investigator may adversely affect the rights, safety, or welfare of the subjects or others, or substantially compromise the research data, **AND**
- Unanticipated: (i.e. unexpected) problems or events are those that are not already described as potential risks in the protocol, consent document, not listed in the Investigator's Brochure, or not part of an underlying disease. A problem or event is "unanticipated" when it was unforeseeable at the time of its occurrence. A problem or event is "unanticipated" when it occurs at an increased frequency or at an increased severity than expected, **AND**
- Related: A problem or event is "related" if it is possibly related to the research procedures.

#### Adverse Event

An untoward or undesirable experience associated with the use of a medical product (i.e. drug, device, biologic) in a patient or research subject.

#### Serious Adverse Event

Adverse events are classified as serious or non-serious. Serious problems/events can be well defined and include;

- death
- life threatening adverse experience
- hospitalization
- inpatient, new, or prolonged; disability/incapacity
- persistent or significant disability or incapacity
- birth defect/anomaly

and/or per protocol may be problems/events that in the opinion of the sponsor-investigator may have adversely affected the rights, safety, or welfare of the subjects or others, or substantially compromised the research data.

All adverse events that do not meet any of the criteria for serious, should be regarded as **non-serious adverse events**.

### **Adverse Event Reporting Period**

For this study, the study treatment follow-up period is defined as 30 days following the last administration of study treatment.

### **Preexisting Condition**

A preexisting condition is one that is present at the start of the study. A preexisting condition should be recorded as an adverse event if the frequency, intensity, or the character of the condition worsens during the study period.

### **General Physical Examination Findings**

At screening, any clinically significant abnormality should be recorded as a preexisting condition. At the end of the study, any new clinically significant findings/abnormalities that meet the definition of an adverse event must also be recorded and documented as an adverse event.

A thorough baseline screening will be followed for all subjects and is outlined in Table-2. A detailed list of the methods in which baseline screening will be performed is outlined in Supplemental 2. All blood draws and safety assessments must be performed **prior** to study treatment administration. Appropriate safety assessments (e.g., evaluation of AEs and SAEs) should be repeated after dosing with study treatment. A physical examination, including general appearance and vital signs, will be performed as indicated in Table-2. If indicated, based on medical history and/or symptoms, additional exams will be performed at the discretion of the investigator. If possible, the same member of the study site staff throughout the study will perform assessments for an individual subject. Information for all physical examinations will be included in the source documentation at the study site. Significant findings that are present prior to the subject signing informed consent will be included in the Medical History. Significant findings made after the signing of the informed consent, which meet the definition of an AE, must be recorded as an AE. Vital signs (blood pressure, pulse, height, weight) will be assessed at each physical examination as indicated in Table-2 (see Supplemental 2 for details on how to acquire vital signs). Whether action needs to be taken to address notable vital signs will be decided by the investigator, considering the overall status of the subject.

### **Supplemental 1: Appropriateness of Measures**

**Skin Scoring:**

There are no validated skin scoring systems for NL. One prior publication developed a non-validated NL skin scoring system (0-12) which examines erythema, infiltration, ulceration, and pain. We will use other simple measures of BSA which is objective and PGA which is well validated in other inflammatory skin conditions. Additionally, we will simply annotate the number of lesions on the individual as a marker of total disease burden.

**Itch Scoring:**

The NRS and Skindex-16 are all well validated measure of itch. The First score measure focuses in upon a gestalt of itch. The later scoring system focuses in upon the itch and its impact upon quality of life.

**Supplemental 2: Safety Measures****Baseline Screening:**

A serum  $\beta$ -hCG test will be performed in all pre-menopausal women as indicated. All pre-menopausal women who are not sterile at screening will also have a urine pregnancy test performed locally as indicated. Any woman with a confirmed positive pregnancy test during screening is not eligible for the study. A positive urine pregnancy test during the treatment periods of the study requires immediate interruption of study treatment until serum  $\beta$ -hCG is performed and found to be negative. If the serum  $\beta$ -hCG test is positive, study treatment must be definitively discontinued.

**Blood Pressure and Pulse:****Height and Weight:**

Height and body weight will be measured in indoor clothing, but without shoes. If possible, body weight assessments should be performed by the same study site staff member and using the same scale throughout the study.

**Blood Draws:**

Subjects should avoid smoking within the hour preceding the blood draws. All laboratory studies will be conducted within the Mayo Clinic Health Systems (Mayo Clinic Arizona and Mayo Clinic Rochester). Details on the collections, shipment of samples and reporting of results will follow Mayo Clinic's current protocols. For the identification of notable values, the Mayo Clinic reference laboratory should be consulted.

### **Supplemental 3: Safety Monitoring**

#### **Infection monitoring:**

Study subjects will be evaluated at each visit for signs or symptoms of infection.

- Vitals signs as well as constitutional symptoms will be assessed.
- Assessment for common infections such as cellulitis as well as oral, vaginal, and cutaneous candidiasis will be performed

#### **Post-study Adverse Event**

All unresolved adverse events should be followed by the sponsor-investigator until the events are resolved, the subject is lost to follow-up, or the adverse event is otherwise explained. At the last scheduled visit, the sponsor-investigator should instruct each subject to report, to the sponsor-investigator, any subsequent event(s) that the subject, or the subject's personal physician, believes might reasonably be related to participation in this study.

#### **Abnormal Laboratory Values**

A clinical laboratory abnormality should be documented as an adverse event if

- they induce clinical signs or symptoms,
- they are considered clinically significant,
- they require therapy.

Laboratory studies will be drawn as indicated in Table-2. Whether action needs to be taken to address notable laboratory values will be decided by the investigator, considering the overall status of the subject. Hematology assessments will be measured at all scheduled study visits specified in Table-2. Serum chemistry will be a comprehensive metabolic panel will be measured at all scheduled study visits specified in Table-2.

#### **Hospitalization, Prolonged Hospitalization or Surgery**

Any adverse event that results in hospitalization or prolonged hospitalization should be documented and reported as a serious adverse event unless specifically instructed otherwise in this protocol. Any condition responsible for surgery should be documented as an adverse event if the condition meets the criteria for an adverse event.

Neither the condition, hospitalization, prolonged hospitalization, nor surgery are reported as an adverse event in the following circumstances:

- Hospitalization or prolonged hospitalization for diagnostic or elective surgical procedures for a preexisting condition. Surgery should **not** be reported as an outcome of an adverse event if the purpose of the surgery was elective or diagnostic and the outcome was uneventful.

#### **8.2 Recording of Adverse Events**

At each contact with the subject, the study team must seek information on adverse events by specific questioning and, as appropriate, by examination. Information on all adverse events

should be recorded immediately in the source document, and also in the appropriate adverse event section of the case report form (CRF). All clearly related signs, symptoms, and abnormal diagnostic, laboratory or procedure results should be recorded in the source document.

All adverse events occurring during the study period must be recorded. The clinical course of each event should be followed until resolution, stabilization, or until it has been ultimately determined that the study treatment or participation is not the probable cause. Serious adverse events that are still ongoing at the end of the study period must be followed up, to determine the final outcome. Any serious adverse event that occurs during the Adverse Event Reporting

Period and is considered to be at least possibly related to the study treatment or study participation should be recorded and reported immediately.

### **8.3 Reporting of Serious Adverse Events and Unanticipated Problems**

When an adverse event has been identified, the study team will take appropriate action necessary to protect the study participant and then complete the Study Adverse Event Worksheet and log. The sponsor-investigator will evaluate the event and determine the necessary follow-up and reporting required.

#### **8.3.1 Sponsor-Investigator reporting: notifying the Mayo IRB**

The sponsor-investigator will report to the Mayo IRB any UPIRTSOs and Non-UPIRTSOs according to the Mayo IRB Policy and Procedures.

Action taken regarding treatment

##### **AE Action:**

All adverse events should be treated appropriately. Treatment may include one or more of the following:

- No action taken (i.e. further observation only)
- [study/investigational] treatment dosage adjusted/temporarily interrupted
- [study/investigational] treatment permanently discontinued due to this adverse event
- concomitant medication given
- non-drug therapy given
- patient hospitalized/patient's hospitalization prolonged

##### **AE Outcome:**

- All AE outcomes should be recorded (not recovered/not resolved; recovered/resolved; recovering/resolving, recovered/resolved with sequelae; fatal; or unknown)

### **Serious Adverse Events (SAE)**

An SAE is defined as any adverse event (appearance of (or worsening of any pre-existing) undesirable sign(s), symptom(s) or medical conditions(s) which meets any one of the following criteria (Life-threatening in the context of a SAE refers to a reaction in which the patient was at risk of death at the time of the reaction; it does not refer to a reaction that hypothetically might have caused death if more severe.):

- Is fatal or life-threatening
- Results in persistent or significant disability/incapacity
- Constitutes a congenital anomaly/birth defect
- 
- Requires inpatient hospitalization or prolongation of existing hospitalization, unless hospitalization is for:
  - Routine treatment or monitoring of the studied indication, not associated with any deterioration in condition (specify what this includes)
  - Elective or pre-planned treatment for a pre-existing condition that is unrelated to the indication under study and has not worsened since signing the informed consent
  - Treatment on an emergency outpatient basis for an event not fulfilling any of the definitions of a SAE given above and not resulting in hospital admission
  - Social reasons and respite care in the absence of any deterioration in the patient's general condition
- Is medically significant, i.e. defined as an event that jeopardizes the patient or may require medical or surgical intervention.

